### 12.2.2 Full Analysis Set

Full Analysis Set (FAS) will include all eyes with successful refractive surgery having at least 1 postoperative visit. The primary analysis set for effectiveness analysis will be the FAS.

## 12.3 Demographic and Baseline Characteristics

Demographic and baseline characteristics will be summarized for each subject. Appropriate summary statistics will be presented for each characteristic. These summaries will be based on the SAF and the FAS.

## 12.4 Refractive Stability

Stability analyses will be performed on eyes that have every follow-up exam from 1 month up to the stability time point [REDACTED] as well as on the eyes that have 2 consecutive exams, but not necessarily every follow-up exam. The following stability analyses will be performed for the time intervals between all consecutive pairs of scheduled postoperative refractions:

- Percentage of eyes that achieve:
  - a change of  $\leq 1.00$  D of MRSE between two refractions performed at 1 month and 3 months, and between subsequent refractions performed at least 3 months apart;
  - a change of  $\leq 0.50$  D of MRSE between two refractions performed at 1 month and 3 months, and between subsequent refractions performed at least 3 months apart;
- Mean overall change and change per month in MRSE between consecutive scheduled visits as determined by a paired analysis;
- Mean  $\pm$ SD MRSE for the preoperative and each postoperative visit;
- Assessment of cylinder stability for correction of spherocylindrical refractive errors

Refractive stability is achieved at the latter of two postoperative manifest refractions performed at least 3 months apart or at 3 months after surgery when compared with the 1-month interval, when all of the following recommended criteria are met:

- At least 95% of the treated eyes have a change  $\leq 1.00$  D of MRSE between the 2 refractions;
- The mean rate of change in MRSE, as determined by a paired analysis, is  $\leq 0.5$  D per year (0.04 D/month) over the same time period;
- The mean rate of change of MRSE decreases monotonically over time, with a projected asymptote of zero or a rate of change attributable to normal aging;
- The 95% confidence interval for the mean rate of change in MRSE includes zero or a rate of change attributable to normal aging; and
- Stability is confirmed at least 3 months after the stability time point by a statistically adequate subgroup [REDACTED].

The primary effectiveness endpoints for the study can only be evaluated once refractive stability has been established [REDACTED], as well as on the eyes that had 2 consecutive exams, but not necessarily every follow-up exam.

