## 10.2.12 Manifest / Subjective Refraction: Efficacy and Safety Assessment

Visit 0, 2/2A – 7/7A, Early Exit

Perform manifest refraction under photopic lighting conditions and measure vertex distance using a phoropter.

*Note:* The chart used for subjective manifest refraction depends on intended use of the data:

- For Inclusion stability at Screening (Visit 0) – performed on site chart
- For VA testing - performed on Sponsor provided electronic chart
- See MOP for more details.

*Note:* Refraction for Inclusion Criteria 4 for hyperopic and astigmatic range must come from the manifest refraction.

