#### 12.5.1.2 Analysis Methods

The FAS will be used for this analysis. The number and percentage of eyes meeting each of the primary effectiveness endpoints will be calculated. The effectiveness criteria will be considered to have been met if the percentage meets or exceeds the target rate at the time of

refractive stability for all primary effectiveness endpoints. These analyses will be performed for the whole FAS as well as stratified by preoperative MRSE subgroups. An analysis will be performed once refractive stability is achieved; a final summary of these endpoints will be performed once the one-year follow-up is complete.

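### Does the falling-rate criterion for refractive stability need a computing rule before the two primary tests can be relied on?

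*Protocol*

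**What the plan says.** Protocol 12.4 and SAP 2.1.2.1 carry the same five criteria for refractive stability and require all of them. The gate on the primary analysis is explicit: "The primary effectiveness endpoints for the study can only be evaluated once refractive stability has been established". Stability is dated to the later of two refractions at least 3 months apart, or to 3 months when compared with 1 month.

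The criterion at issue is the third: "The mean rate of change of MRSE decreases monotonically over time, with a projected asymptote of zero", or a rate attributable to normal aging. The first two criteria name their interval; the second, for example, applies "over the same time period". The third names none.

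The descriptive stability analyses are done "for the time intervals between all consecutive pairs of scheduled postoperative refractions". Refraction is scheduled at "Visit 0, 2/2A – 7/7A, Early Exit" (Protocol 10.2.12), which includes the 1-week visit, but the cohort with every exam is counted from 1 month. The fifth criterion deals with later data: "Stability is confirmed at least 3 months after the stability time point by a statistically adequate subgroup" (the rest of that line is redacted).

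On timing, Protocol 12.5.1.2 says "An analysis will be performed once refractive stability is achieved" and "a final summary of these endpoints will be performed once the one-year follow-up is complete", whereas Protocol 7.1 places all analyses at study completion. The protocol summary refers the definition of stability to ANSI Z80.11-2012 (R2017) F.3.

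**The concern.** A rate that falls over time can be checked in at least three ways:

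- (a) The rate for the interval ending at the candidate visit is below every earlier rate.
- (b) Every successive rate up to that visit falls.
- (c) The whole series to month 12 falls.

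The series could also start at 1 week or at 1 month. At month 3 only one interval from 1 month exists, so there is nothing for it to fall from.

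The trial is single-arm and unmasked, and Protocol 7.1 puts analysis at the end, when every visit's results are known. If the reading were chosen then, and if it decided whether and where Tests 1 and 2 are run, a registration result could depend on a choice made with outcomes in view. Reading (c) looks especially damaging, because eyes with no drift at all would nearly always fail it. A second worry is that stability first met at month 12 cannot be confirmed within the study, and no sentence says what then happens to the tests.

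**Working it through.** **The plan's own figure.** The rate limit is 0.5 D per year: 0.5 / 12 = 0.0417 D/month, which agrees with the printed 0.04. The falling-rate criterion has no figure of its own.

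**Do the readings choose different visits?** Let r1, r2, r3, r4 be the absolute mean monthly rates over 1-3, 3-6, 6-9 and 9-12 months.

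- Month 3: there is no earlier interval, so (a) and (b) both pass by default.
- Month 6: both require r2 < r1, so they are identical.
- Month 9: (a) requires r3 < r1 and r3 < r2; (b) requires r1 > r2 > r3. Whatever passes (b) passes (a).
- The other criteria and the confirmation are the same under both. So if (b) declares stability, (a) declares it at the same visit. The only possible difference is that (a) declares at month 9 and (b) never does.
- If (c) holds, all four rates are in order, so (a) and (b) hold at every visit. Where (c) declares, (a) and (b) declare at the same visit.

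Illustration: with r1, r2, r3 = 0.010, 0.020, 0.005 D/month, month 6 fails under both and month 9 passes (a) but fails (b). With 0.020, 0.010, 0.012, both pass at month 6 and both fail at month 9.

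**How often does it matter?** The documents give 25 subjects followed (50 eyes), the visit schedule and the thresholds. Assumed, because the documents do not give them: visit SD 0.20-0.30 D, fellow-eye correlation 0.3-0.7, the drift patterns below, zero in the confidence-interval criterion, and confirmation meaning that the next interval meets the 95%, rate and confidence-interval criteria. Each setting had 20,000 simulated trials. Percentage in which stability is not met and confirmed by month 12:

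| True rate by interval (D/month) | (a) | (b) | (c) |
|---|---|---|---|
| none | 2%-16% | 4%-20% | 91%-92% |
| 0.06 / 0.03 / 0.01 / 0.005 | 12%-28% | 26%-40% | 74%-88% |
| 0.10 / 0.03 / 0.01 / 0.005 | 10%-28% | 13%-34% | 67%-83% |

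Without the third criterion, the no-drift figure is 1%-11%. At the noisiest setting (SD 0.30 D, correlation 0.7), the criterion adds 16.4 - 11.2 = 5.2 points under (a) and 19.5 - 11.2 = 8.3 points under (b). Readings (a) and (b) give different outcomes in 1%-14% of trials, and different visits when both declare in 0.0%. A separate rerun under these assumptions gave the same pattern.

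**Why (c) stands apart.** If four rates near zero were exchangeable, strict order would occur in 1/4! = 1/24, about 4% of trials. The first interval is 2 months rather than 3, so its rate is noisier and more often the largest, and about 8%-9% pass. Readings (a) and (c) differ in 54%-89% of trials for this reason alone.

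**Does the text support (c) or a 1-week start?** Stability is dated to the later of two refractions, and later data have their own criterion, the confirmation. Under (c) the third criterion would govern those later data as well. A projected asymptote also implies extrapolating from the data so far. A 1-week start could move the declared visit, in about 2%-10% of trials, but the cohort, the change criteria and the earliest candidate visit all run from 1 month.

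**Month 12.** Confirmation is one of the required criteria and comes at least 3 months later, while the last visit is the 12-month visit. Stability first met there is therefore not established, and the gate sentence already says the endpoints cannot then be evaluated.

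**The case for a change.** The best case for a change is that a gate on both primary tests should be computable from the SAP, which repeats the protocol's words without adding a rule. No redaction falls inside this criterion. Protocol 6.5 says the definitions are in Section 12.4, so a reader should not need the standard. The trial is open-label, and a sentence or two before database lock would cost little.

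Other readings can also be built. If at least two intervals were required, month 3 could never qualify; in a separate simulation (no drift, SD 0.25 D, correlation 0.5), stability was then never declared in 42.6% of trials, against 9.6% when month 3 passes by default. With signed rates, a drift of -0.2 D gave 59.4% never declared, against about 22% on absolute rates.

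What stands is that the visible text leaves the intervals, the handling of month 3 and the projection of the asymptote unwritten, and that Protocol 7.1 and 12.5.1.2 are worded differently on timing. The more extreme readings do not stand. The definition expressly allows month 3 against 1 month, so a two-interval requirement contradicts it. An asymptote of zero makes sense as a shrinking size of change, so a negative rate moving towards zero is falling in the intended sense. As to timing, Protocol 7.1 says when analyses are run; it does not decide which intervals count. No effect on a Test 1 or Test 2 conclusion, or on type I error, has been shown.

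**Conclusion.** The concern does not call for a change. It identifies a rule that is not spelled out; it does not show a rule that gives a wrong answer. The natural application is absolute mean rates from 1 month up to the candidate visit, with later visits used only for confirmation. Choosing between the two natural readings cannot move the tests to a more favourable visit. It can only decide whether month 9 qualifies, in 1%-14% of trials under the assumed variability. With no drift the criterion adds a few points to the chance that stability is not reached, and where there is true drift, part of the failure is the criterion doing its job. The month-12 case follows from the existing gate.

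The percentages rest on assumed SDs, correlations and drift and on a guess at partly redacted confirmation text, so they show sensitivity and do not predict this trial's result. The argument about visits is logical and does not depend on them; it needs only absolute rates, a start at 1 month and month 3 passing by default. The cited ANSI clause or the redacted text may already state the application, and neither could be checked.

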## 12.5 Effectiveness Analyses

### 12.5.1 Analysis of Primary Effectiveness Endpoint(s)

In order to evaluate efficacy of the WaveLight EX500 excimer laser system for the correction of hyperopia with and without astigmatism, the following primary effectiveness endpoints are defined:

- Percentage of eyes with MRSE within  $\pm 0.50$  D at refractive stability\* (Target: > 50%)
- Percentage of eyes with MRSE within  $\pm 1.00$  D at refractive stability\* (Target: > 75%)

#### 12.5.1.1 Statistical Hypotheses

The statistical test for primary variables will be performed using the exact test of a binomial proportion. The null and alternative hypotheses are:

Test 1:

$$H_0: \pi_1(\text{EX500}) = 50.0\%$$

$$H_1: \pi_1(\text{EX500}) > 50.0\%$$

Test 2:

$$H_0: \pi_2(\text{EX500}) = 75.0\%$$

$$H_1: \pi_2(\text{EX500}) > 75.0\%$$

where  $\pi_1(\text{EX500})$  is the population proportion of eyes in the EX500 group with MRSE within  $\pm 0.50$  D at refractive stability, and  $\pi_2(\text{EX500})$  is the population proportion of eyes in the EX500 group with MRSE within  $\pm 1.00$  D at refractive stability. The constants 50.0% in Test 1 and 75.0% in Test 2 are the target levels for these MRSE parameters referred to from the FDA Checklist of Information Usually Submitted in an IDE (1996).

The p-values will be provided for Test 1 and Test 2. [REDACTED]

[REDACTED]

[REDACTED]

[figure not shown]
[REDACTED]

[REDACTED]

#### 12.5.1.2 Analysis Methods

The FAS will be used for this analysis. The number and percentage of eyes meeting each of the primary effectiveness endpoints will be calculated. The effectiveness criteria will be considered to have been met if the percentage meets or exceeds the target rate at the time of

refractive stability for all primary effectiveness endpoints. These analyses will be performed for the whole FAS as well as stratified by preoperative MRSE subgroups. An analysis will be performed once refractive stability is achieved; a final summary of these endpoints will be performed once the one-year follow-up is complete.

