Assessment(s)	
Effectiveness
  

Manifest refraction

 
Safety
 

Patient reported outcome

Best corrected photopic distance visual acuity (BCDVA)

Manifest refraction

Intraocular pressure (IOP)

Slit lamp examination

Dilated fundus examination

 
Study Design	
This is a prospective, single-arm, multi-center, interventional study with planned bilateral treatment.
 
Qualified subjects will receive bilateral LASIK treatment and be followed for 1 year. Subjects will be asked to attend a total of 9 visits (screening, surgery, day 1, 1 week, 1 month, 3 month, 6 month, 9 month, and 1 year). Total expected duration of subject participation is approximately 1 year.

Subject population	
Subjects 18 years of age or older who desire to have LASIK will be consented and screened for meeting the inclusion and exclusion criteria.
 
Planned number of subjects enrolled/consented: approximately 70 eyes (35 subjects)
 
Planned number of treated/randomized subjects: approximately 60 eyes (30 subjects)

	
Planned number of completed subjects: approximately 50 eyes (25 subjects)

Key inclusion criteria  (See Section 8.1 for a complete list of inclusion criteria)	
Subjects must meet all inclusion criteria as listed in Section 8.1.
 
Key Inclusion Criteria include:
 

• Hyperopia up to +3.0 D of sphere with and without astigmatic refractive error up to +3.0 D at the spectacle plane, with a maximum MRSE of +3.0 D

• Intended to treat bilaterally

• Best corrected photopic distance visual acuity of 20/20 or better

• Uncorrected photopic distance visual acuity of 20/40 or worse

• Stable refraction (within <math>\pm 0.50</math> D), as determined by MRSE for a minimum of 12 months prior to surgery

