Key exclusion criteria  (See Section 8.2 for a complete list of exclusion criteria)	
Subjects must not meet exclusion criteria as listed in Section 8.2.
 
Key Exclusion Criteria include:
 

• History or evidence of active or inactive corneal disease or retinal vascular disease, keratoconus, glaucoma (or suspect), or cataract

• Previous intraocular or corneal surgery

• Intent to have monovision treatment

• Increased risk for developing strabismus post-treatment

Data analysis and sample size justification	
The safety analysis set (SAF) will include all eyes for which refractive surgery is attempted with test device (regardless of success or failure). Full Analysis Set (FAS) will include all eyes with successful refractive surgery having at least 1 postoperative visits. The primary analysis set for effectiveness analysis will be the FAS.
 
[REDACTED]
 
[REDACTED]
 
[REDACTED]

Subject evaluability will be determined prior to locking database. No interim analysis is planned.

In order to evaluate efficacy of the WaveLight EX500 excimer laser system for the correction of hyperopia with and without astigmatism, the following primary effectiveness analyses will be conducted.

Test 1: Percentage of eyes with MRSE within  $\pm 0.50$  D at refractive stability is greater than the target level of 50%

Test 2: Percentage of eyes with MRSE within  $\pm 1.00$  D at refractive stability is greater than the target level of 75%.

For the statistical test of primary effectiveness variables, the exact test of a binomial proportion will be used, and the p-values will be provided for Test 1 and Test 2.

Type 1 error at each test is set as one-sided 2.5%.

Refractive surgery will be bilaterally performed for all subjects. Both eyes from each subject will be used for analysis.

	
Each safety variable will be summarized descriptively. Incidence of adverse events will be calculated.

Key words	

• LASIK

• Hyperopia

• Astigmatism

Associated materials	

• WaveLight EX500 Laser System

• WaveCard

**Table 3–1** Schedule of Study Procedures and Assessments

[figure not shown]
	Screening 	Surgery	Postoperative							Other	

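### Effectiveness is declared on a point estimate at or above target, which contradicts the one-sided 2.5% exact tests and gives a false-success rate of about 50%

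*Protocol*

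**What the plan says.** Protocol 12.5.1.1 and SAP 4.2 set up a conventional one-sample test for each primary endpoint. The null value is 50% for MRSE within ±0.50 D and 75% for MRSE within ±1.00 D, with one-sided alternatives above those values. On method: "The statistical test for primary variables will be performed using the exact test of a binomial proportion". On the null values: "The constants 50.0% in Test 1 and 75.0% in Test 2 are the target levels for these MRSE parameters". The Protocol Summary adds: "Type 1 error at each test is set as one-sided 2.5" percent. SAP Table 4-1 lists the exact binomial test as the method for both endpoints.

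The decision is stated separately, in Protocol 12.5.1.2 and in the same words in SAP 4.3: "The effectiveness criteria will be considered to have been met if the percentage meets or exceeds the target rate". The rule is applied once stability is reached, and both endpoints have to satisfy it. It mentions no p-value, confidence limit or alpha. In the readable text the p-values are only reported: "The p-values will be provided for Test 1 and Test 2". The SAP's list of decision criteria for study success gives the endpoints and their targets and no test criterion.

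The endpoints themselves are written with strict targets (> 50% and > 75%), whereas the decision sentence also accepts a result exactly at target.

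**The concern.** The plan has two success rules that give different answers. One is a hypothesis test with 2.5% error control. The other asks only that the observed percentage reach the null value. If a true rate equals the null value, the observed percentage reaches it about half the time, so the stated 2.5% does not apply to the decision as written.

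This is the trial's only primary effectiveness decision, and the study is meant to support registration in Japan. Over a wide range of plausible results (25 to 32 of 50 for ±0.50 D, 38 to 43 of 50 for ±1.00 D), an endpoint passes under one rule and fails under the other. Whether the trial succeeded would then depend on which section is read.

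**Working it through.** **Inputs**
- Null proportions 50% and 75%; exact binomial test (Protocol 12.5.1.1, SAP 4.2).
- One-sided alpha 0.025 per test (Protocol Summary).
- Success: observed percentage ≥ target on both endpoints (Protocol 12.5.1.2, SAP 4.3).
- Eyes: "Planned number of completed subjects: approximately 50 eyes (25 subjects") and "Planned number of treated/randomized subjects: approximately 60 eyes (30 subjects"). I use n = 50, with n = 60 as a check.
- Assumption: eyes are independent, as the exact test itself assumes. Correlation is examined in step 5.

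**1. Does the exact test deliver the stated 2.5%?** The critical count is the smallest r with P(X ≥ r | n, p₀) ≤ 0.025, where X is binomial.

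| n | p₀ | critical count | attained alpha |
|---|---|---|---|
| 50 | 0.50 | 33 (66.0%) | 0.0164 |
| 50 | 0.75 | 44 (88.0%) | 0.0194 |
| 60 | 0.50 | 39 (65.0%) | 0.0137 |
| 60 | 0.75 | 52 (86.7%) | 0.0212 |

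So the tests, used as the decision rule, keep each error at or below 2.5%.

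**2. What does the written rule deliver?** The threshold is r = ⌈p₀n⌉, and the false-pass probability is P(X ≥ r | n, p₀).

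| n | p₀ | count needed | P(pass) when the true rate is p₀ |
|---|---|---|---|
| 50 | 0.50 | 25 | 0.556 |
| 50 | 0.75 | 38 | 0.511 |
| 60 | 0.50 | 30 | 0.551 |
| 60 | 0.75 | 45 | 0.569 |

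Reading the rule strictly as above target changes little. At n = 50 the ±0.50 D figure falls to 0.444 (26 needed) and the ±1.00 D figure stays at 0.511, because 75% of 50 is 37.5 and cannot be observed. At n = 60 the figures are 0.449 and 0.451.

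**3. Both endpoints together.** An eye within ±0.50 D is also within ±1.00 D, so each eye falls in one of three cells with probabilities π₁, π₂ − π₁ and 1 − π₂. Summing the trinomial over counts that pass both thresholds, at n = 50:

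| True rates (±0.50 D / ±1.00 D) | Written rule | Both exact tests |
|---|---|---|
| 50% / 75% (both at null) | 38.1% | 0.36% |
| 65% / 75% (only ±1.00 D at null) | 51.1% | 1.9% |
| 50% / 90% (only ±0.50 D at null) | 55.6% | 1.6% |

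At n = 60 with both rates at null the written rule gives 41.1%. The type I error of a rule that needs both endpoints is its worst case over the null, where one endpoint is at its null and the other is nearly certain to pass. That is the single-endpoint figure in step 2.

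**4. A result on which the rules disagree.** 30/50 (60%) and 40/50 (80%) both exceed target. The exact one-sided p-values are P(X ≥ 30 | 50, 0.50) = 0.10 and P(X ≥ 40 | 50, 0.75) = 0.26.

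**5. Correlation between a subject's two eyes.** Simulation over an assumed correlation of 0 to 1, with 25 or 30 subjects, gives 0.50 to 0.57 per endpoint for the written rule. The conclusion does not depend on independence.

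**The case against.** The strongest objection is the redaction. Text is blacked out after the statement on p-values in Protocol 12.5.1.1 and SAP 4.2, directly after the success sentence in SAP 4.3, and in the data analysis and sample size part of the Protocol Summary. A p-value rule or a qualification may sit there, so the public version cannot show that the full plan lacks one. It does show two readable statements that conflict. A hidden test-based rule would leave the unqualified point-estimate sentence in place and add a second rule beside it.

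It can also be said that the sentence is loose wording for a test-based decision, since Table 4-1 in the same SAP section names the exact test. Or it may be a deliberate benchmark check, since 50% and 75% are called target levels taken from the FDA checklist. Both readings are possible. On the first, the sentence is wrong as written. On the second, the hypotheses and the 2.5% alpha serve no decision, although the plan uses those same targets as null values. Each reading needs an edit.

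Three narrower points stand. The figure of about 50% is the worst case for the two-endpoint rule; with both rates at target it is 38% to 41%. The mismatch between the strict targets and a rule that accepts equality is minor, mattering at n = 50 only for exactly 25/50. And the exact test ignores pairing of eyes: at an assumed inter-eye correlation of 0.5 its simulated alpha is 0.036 to 0.050. That is a separate matter, and it does not rescue the written rule.

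**Conclusion.** The concern holds. The readable success rule contradicts the exact tests and the 2.5% error rate that the plan sets for them. At the planned 50 eyes, treated as independent, the written rule's false-pass probability is 55.6% and 51.1% per endpoint, against 1.64% and 1.94% under the tests. For the joint decision it is 38.1% with both rates at target and about 51% to 56% in the worst case. These figures take the sentence literally as the decision rule. They need no assumption about redacted text beyond the fact that such text cannot remove a sentence that is printed. This must be corrected, because the primary conclusion is otherwise open to two answers.

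**What to change.** In Protocol 12.5.1.2 and SAP 4.3, replace the success sentence with: the effectiveness criteria are met if the one-sided exact binomial p-value is below 0.025 for both Test 1 and Test 2; equivalently, the lower one-sided 97.5% exact (Clopper-Pearson) confidence limits exceed 50% and 75%. Put the same rule under the decision criteria for study success in the SAP's executive summary, and label the comparison of the observed percentage with the target as descriptive. If redacted text already holds a decision rule, bring it into line with this one.

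The edit is wording only and adds no subjects, visits or data. It does raise the bar from 25/50 and 38/50 to 33/50 and 44/50, which is the bar that the stated alpha already implies. The sponsor should confirm that the sample size was set for that bar, because no assumed true rates are readable. As an assumed range, with 50 independent eyes, the probability of passing both tests is 27% at true rates of 65%/85%, 66% at 70%/90%, 75% at 75%/90% and 98% at 80%/95%. Under the written rule it is at least 96% in each case.
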